## **Outcome measures**

Patient variables recorded will be maternal age, infertility duration and etiology, BMI, AFC, and endometrial thickness. The treatment cycle variables recorded were oocyte number, mature oocyte number, blastocyst number (i.e., the number usable blastocysts, with grade  $\geq 2$ BB), oocyte maturity, oocyte fertilization, blastocyst rate (i.e., the ratio of the number of blastocysts to the number of 2PN zygotes). The primary outcome measure recorded will be LB (changed from ongoing pregnancy),

with clinical pregnancy and miscarriage as secondary outcomes. A LB cycle will be defined as a pregnancy cycle that delivered at >20 weeks of gestation, resulting in a live infant. A clinical pregnancy will be defined as a cycle with a fetal sac observed on ultrasound after 5 weeks of gestation. A biochemical pregnancy will be defined as a cycle with an arbitrary serum  $\beta$ hCG concentration of >29 IU/L. Pregnancy tests will be performed 9 days after the FET.

## **Statistics**

Statistical Package for Social Science 11.5 (SPSS version 11.5) was used for the statistical analysis of characteristics and outcome measures (i.e., p values and Risk Ratios (RR)). Continuous data were analyzed either with the student's t-test or Mann-Whitney-U test, depending on outcome of normality testing (Shapiro-Wilk). Categorical data were analyzed using either the chi-square test or Fisher's Exact-test (i.e., for low sample numbers). A  $p < 0.05$  indicated outcomes of significant difference.

### *Sample size calculation*

At the trial centre the overall ongoing pregnancy rate was 66% for the transfer CCS euploid blastocysts, while the overall ongoing pregnancy rate was 52% for blastocysts selected for transfer by morphology only. The sample sizes required to have 80% chance of detecting a difference of 20% at a significance level of 0.05 was calculated to be 74.

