**Changes to original registration:**

**Primary outcome measure:** the primary outcome measure was changed from ongoing pregnancy (i.e., clinical pregnancy at  $>14$  weeks of gestation) to the preferred outcome of live birth (LB, a delivery at  $>20$  weeks, with a live infant).

The AFC cut-off was changed to  $\geq 5$  (changed from  $\geq 10$ ) to be in line with the definition of decreased ovarian reserve and increase the eligible population.

**Trial registration:** ClinicalTrials.gov ID: NCT03095053

Protocol submission: 23 March 2017

Protocol revised submission: 28 March 2017

Randomized Controlled Trial registered and posted: 29 March 2017

Data collection start: 21 February 2018

Data collection was commenced at  $>20$  weeks from the date of last patient randomized had undergone FET

Data analysis start: 25 April 2018

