## **Materials and methods**

### **Study design**

The RCT will be performed as a single private IVF center trial. The patient population of the trial will include young patients undergoing autologous blastocyst freeze-all IVF cycles from March 2017. In this trial, a patient will undergo a blastocyst-freeze-all cycle after ICSI and only the reproductive outcomes of the first FET following the freeze-all will be analyzed. Currently at the trial centre more than 95% of cycles are extended culture cycles and more than 80% of these cycles result in freeze-all cycles, with a live birth rate after the first FET of >45% per oocyte retrieval.

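### The sample-size justification was not updated when live birth became primary, so the stated 80% power is not established for that outcome

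*Combined protocol and SAP*

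**What the plan says.** The section on changes to the original registration records that "the primary outcome measure was changed from ongoing pregnancy" (a clinical pregnancy beyond 14 weeks) to live birth. Outcome measures agrees: "The primary outcome measure recorded will be LB (changed from ongoing pregnancy"). The Objectives section and Figure 1 also name live birth as primary.

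The Sample size calculation, which is current text, has no live-birth figure. It gives "At the trial centre the overall ongoing pregnancy rate was 66% for the transfer CCS euploid blastocysts" and "the overall ongoing pregnancy rate was 52% for blastocysts selected for transfer by morphology only". It continues: "The sample sizes required to have 80% chance of detecting a difference" of 20% at the 0.05 level, with a result of 74. It does not say whether the test is one- or two-sided, or whether 74 is per arm or in total.

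The only live-birth rate in the document is in Study design, "with a live birth rate after the first FET of >45% per oocyte retrieval". The sample size does not use it.

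Eligibility criteria restricts the trial to women aged 35 or younger with an antral follicle count of at least 5 and at least two 2BB blastocysts on day 5. The follicle-count limit was lowered from 10. Under Randomisation, a PGT couple whose biopsied blastocyst is aneuploid receives the next best blastocyst by morphology, which has not been tested.

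**The concern.** Superiority will be claimed on live birth, so that is the outcome for which a reader needs the power and the detectable difference. The plan gives both only for the superseded outcome, and the supporting rates have two further gaps.

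- **Source population.** Both rates are called *overall*, a word the plan does not define. Nothing shows that they come from couples like those enrolled.
- **Unit.** The 66% is a rate per euploid transfer. The randomised PGT arm mixes euploid transfers with transfers of untested blastocysts, so 66% is not an expected rate for that arm even on ongoing pregnancy.

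The practical risk lies in interpretation. A non-significant live-birth result could be read as coming from a trial with 80% power for that outcome, which the plan does not show.

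**Working it through.** **Inputs from the plan.** Ongoing-pregnancy rates of 52% and 66%, target difference 20% (read as percentage points), power 80%, significance level 0.05, size 74 (all from Sample size calculation); 1:1 allocation (Randomisation).

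**Inputs that are assumptions.** 74 is per arm; the test is two-sided unless marked; a 45% live-birth base is illustrative; the share of ongoing pregnancies that end in live birth (retention, r) is 0.90 to 0.98.

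**Formulas.** Normal approximation with pooled variance under the null. With d = p2 − p1, p̄ the mean of the two rates and n per arm:

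- n = [z_α √(2p̄(1−p̄)) + z_β √(p1(1−p1) + p2(1−p2))]² / d²
- power = Φ{[d − z_α √(2p̄(1−p̄)/n)] / √([p1(1−p1) + p2(1−p2)]/n)}

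**Step 1: reproduce 74.** For 52% v 72%, p̄ = 0.62 and the two square-root terms in n are 0.6864 and 0.6717.

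- One-sided: (1.645 × 0.6864 + 0.842 × 0.6717)² / 0.04 = 71.8, so 72 per arm.
- Two-sided: (1.960 × 0.6864 + 0.842 × 0.6717)² / 0.04 = 91.3, so 92 per arm.

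For 46% v 66% the results are 76 one-sided and 96 two-sided. So 74 is close to a one-sided, per-arm calculation for 20 points. The quoted pair, 52% v 66%, needs 152 one-sided or 193 two-sided. A two-sided result near 74 appears only if 66% is taken as the lower rate (66% v 86% gives 71), which does not fit its role in the plan. Reading 74 as a total (37 per arm) gives 55% one-sided or 42% two-sided power for 52% v 72%.

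**Step 2: power at 74 per arm.** For 52% v 72% the standard errors are 0.6864/√74 = 0.0798 (null) and 0.6717/√74 = 0.0781 (alternative). Two-sided power is Φ[(0.20 − 1.960 × 0.0798)/0.0781] = Φ(0.56) = 71%.

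| Rates | Difference (points) | Two-sided | One-sided |
|---|---|---|---|
| 52% v 72% | 20 | 71% | 81% |
| 45% v 65% (assumed base) | 20 | 69% | 79% |
| 52% v 66% (quoted rates) | 14 | 41% | 53% |

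**Step 3: equal late loss.** Both rates are multiplied by the same r.

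| r | 52% v 72% becomes | Two-sided power | 52% v 66% becomes | Two-sided power |
|---|---|---|---|---|
| 0.98 | 51.0% v 70.6% (19.6 points) | 69% | 51.0% v 64.7% (13.7) | 39% |
| 0.95 | 49.4% v 68.4% (19.0) | 65% | 49.4% v 62.7% (13.3) | 37% |
| 0.90 | 46.8% v 64.8% (18.0) | 60% | 46.8% v 59.4% (12.6) | 33% |

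**Step 4: unequal late loss.** Take r = 0.90 after morphological selection and 0.98 in the PGT arm. Then 52% v 66% becomes 46.8% v 64.7% (17.9 points) and two-sided power rises from 41% to 59%. Likewise 52% v 72% becomes 46.8% v 70.6% (23.8 points) and power rises from 71% to 84%.

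**Step 5: composition of the PGT arm.** If a share e of tested blastocysts is euploid, the arm's expected rate is e × 66% plus (1 − e) times the rate after transfer of the next best, untested blastocyst. The plan gives neither e nor that second rate, so this effect is not quantified here.

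**The case against.** The best defence is that the plan states a detectable difference of 20 points as a target in its own right. It is not 66 minus 52. If 20 points is also the target for live birth, lowering the base from 52% to 45% moves two-sided power only from 71% to 69%, and the requirement from 92 to 96 per arm. The change of outcome is also disclosed, and the sample-size section names the outcome it used. This stands as far as it goes: the switch alone may cost little. But the plan does not say that 20 points is a live-birth target, and it offers no live-birth rate to support one.

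Three stronger readings are tempting, and the documents do not support them.

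- **The rates come from a different population.** *Overall* is undefined. The rates may or may not resemble those of eligible couples; the plan simply does not show it.
- **The stated power must be too high because late losses shrink the difference.** That requires similar loss after 14 weeks in both arms. The trial's own secondary hypothesis is less miscarriage, defined as loss before 20 weeks, after euploid transfer. Step 4 shows that power could then rise.
- **The centre's 45% converts the ongoing-pregnancy rates to live birth.** It is a floor, counted per oocyte retrieval and not split by selection method, so dividing it by a 52% rate for transferred blastocysts does not give a retention rate.

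**Conclusion.** The point holds as a gap in justification, not as an error of arithmetic on the outcome. The stated 80% power with 74 rests only on ongoing-pregnancy rates of undefined source, one of them for a subgroup of the PGT arm, and is not established for live birth.

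At an assumed 74 per arm and two-sided 5%, power for 20 points is 71% from a 52% base and 69% from a 45% base; for the quoted 14 points it is 41%. With equal retention of 0.90 to 0.98 in both arms, the ranges are 60–69% and 33–39%. With lower late loss after euploid transfer they could be higher, so the documents do not fix the direction of the change.

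A reader might attribute the whole shortfall from 80% to the outcome switch. Most of it has other causes in the same section: the fall from 81% to 71% is one- against two-sided testing, and the fall from 71% to 41% is 14 against 20 points. Correcting those would still leave a calculation for a superseded outcome.

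**What to change.** Rewrite the Sample size calculation at the existing size:

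- Use live-birth rates after the first FET from the centre's database, for couples who meet the eligibility criteria. Name the source population and period. Use cycles from before the trial, so that the statement is not built on the trial's own results.
- Count per couple of the kind randomised. For the PGT arm, include couples whose tested blastocyst is aneuploid and who receive an untested one.
- State the detectable live-birth difference and the power, the sidedness, and whether 74 is per arm.
- Say that the original calculation used ongoing pregnancy.

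The cost is one query of a database that the trial already uses and one rewritten paragraph. No extra patients are needed. The price is a stated power that may be less favourable than 80%.

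### The sample size targets a 20-point difference without explanation, beside centre rates that differ by 14 points; with 74 per arm, two-sided power is about 70% for 20 points and 41% for 14

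*Combined protocol and SAP*

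**What the plan says.** The Sample size calculation section gives two centre rates: "the overall ongoing pregnancy rate was 66% for the transfer CCS euploid blastocysts", and "the overall ongoing pregnancy rate was 52% for blastocysts selected for transfer by morphology only". The next sentence gives the number needed to "have 80% chance of detecting a difference of 20% at a significance level of 0.05 was calculated to be 74".

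The section does not say where the 20% comes from, whether it is absolute or relative, whether the test is one- or two-sided, or whether 74 is per arm or in total. The Statistics section says "Categorical data were analyzed using either the chi-square test" or Fisher's exact test, at p < 0.05, and mentions no one-sided test. The Randomisation section sets 1:1 allocation.

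**The concern.** The cited rates differ by 66 − 52 = 14 points, and the design difference is 20. The documents give no other pair of PGT and morphology rates. The live-birth rate above 45% in the Study design section has no PGT comparator. No smallest important difference is argued either.

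This is the trial's only power statement, so it is the reader's guide to what a non-significant primary result means. Because the centre's rates stand directly before the calculation, it is easy to assume that the 80% covers a benefit of the size the centre has seen. If it does not, a non-significant result carries much less information than the plan suggests.

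**Working it through.** **Inputs.** Rates of 66% and 52%, a 20% difference, 80% power, 5% significance and 74 (Sample size calculation); 1:1 allocation (Randomisation); chi-square or Fisher's exact test (Statistics). Sidedness and the per-arm reading are assumptions, so each is varied.

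**Formulas.** Let d = p1 − p2, p̄ = (p1 + p2)/2, A = √[2p̄(1 − p̄)] and B = √[p1(1 − p1) + p2(1 − p2)].

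- n per arm = (z_α·A + z_β·B)² / d²
- power = Φ[(d·√n − z_α·A) / B]
- z_β = 0.842 for 80% power; z_α = 1.960 two-sided or 1.645 one-sided.

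**Step 1: reproduce 74.** Take 69% v 49%, which is 20 points apart with the same midpoint as the cited rates: A = 0.6956, B = 0.6810.

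- One-sided: (1.1441 + 0.5732)² / 0.04 = 73.7, so 74 per arm.
- Two-sided: (1.3633 + 0.5732)² / 0.04 = 93.7, so 94 per arm.

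Other 20-point pairs anchored on a cited rate agree:

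| Rates | n per arm, one-sided | n per arm, two-sided | Two-sided power, 74 per arm |
|---|---|---|---|
| 72% v 52% | 72 | 92 | 71% |
| 69% v 49% | 74 | 94 | 70% |
| 66% v 46% | 76 | 96 | 69% |

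Two-sided, 74 appears only at rates far from those cited, for example about 84% v 64%.

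**Step 2: other readings of the stated figures.**

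- 74 in total (37 per arm): power for 20 points is about 41–42% two-sided and 54–55% one-sided.
- 20% relative, upward from 52%: 52 × 1.2 = 62.4%, a gap of 10.4 points. This needs 355 per arm two-sided or 279 one-sided.
- 20% relative, downward from 66%: 66 × 0.8 = 52.8%. This needs 217 per arm two-sided or 171 one-sided.

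None of these gives 74 with 80% power.

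**Step 3: power for the cited rates.** For 66% v 52%, A = 0.6956, B = 0.6885 and d√74 = 0.14 × 8.602 = 1.2043.

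- Two-sided: (1.2043 − 1.3633)/0.6885 = −0.231, so power is 40.9%.
- One-sided: (1.2043 − 1.1441)/0.6885 = 0.087, so power is 53.5%.
- Exact enumeration, two-sided: 42.6% for the uncorrected chi-square and 36.0% for Fisher's test.
- If 74 is the total: 22.9% two-sided and 33.5% one-sided.
- Needed for 80%: 193 per arm two-sided, 152 one-sided.

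**Step 4: detectable difference.** Solving the power formula for 80% with 74 per arm and 52% in the morphology arm gives about 22 points two-sided and about 20 points one-sided.

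**Step 5: why 14 points may itself be too large.** The 66% describes euploid transfers. Under the Randomisation section, a PGT-arm couple whose biopsied blastocyst is aneuploid receives the next-best blastocyst by morphology. The documents give no euploid share. Assume 50% to 70%, with the remaining transfers at 52%. The between-arm difference is then 0.5 × 14 = 7 to 0.7 × 14 = 9.8 points, and two-sided power with 74 per arm is about 13% to 22%. This range is illustrative and rests on those two assumptions.

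**The case against.** A trial may be sized for a difference larger than past experience suggests, and the section never says that the 20% was derived from the 66% and 52%. That stands: the fault there is a missing justification.

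Three stronger readings are tempting, and the documents do not support them.

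- **The plan claims 80% power for 14 points.** It does not. It attaches the 80% to a 20% difference only.
- **The figure of 74 is an arithmetic error.** It is coherent as a per-arm number for 20 absolute points with a one-sided 5% test, where the detectable difference is also about 20 points. The difficulty is that nothing in the plan says the test is one-sided.
- **Repeating the centre's difference would fail to reach significance.** This depends on sidedness. With 74 per arm, 38 v 49 events gives p = 0.066 two-sided and 0.033 one-sided; 39 v 49 gives 0.094 and 0.047.

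Nor does any section say that a non-significant result would be reported as showing no superiority; that would be speculation.

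It is also fair to say that the Statistics section does not use the word two-sided. But a chi-square test at p < 0.05 with no direction mentioned is ordinarily two-sided, and under that reading the stated 80% is not met even for 20 points.

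**Conclusion.** The concern holds in this form. The 20-point target is unexplained beside rates 14 points apart, and the power statement is correct only under a one-sided test that the plan does not specify.

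The main figures assume 74 per arm and a two-sided 5% chi-square test. The text states neither. The per-arm reading is supported by the plural in "The sample sizes required to have 80% chance of detecting" and by the failure of 74 in total to come near 80%. The two-sided reading follows from the ordinary use of the planned test.

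The conclusion about the cited rates does not depend on these choices. Power for 66% v 52% is between 36% and 54% across the per-arm variants, and lower if 74 is the total. Even these figures concern ongoing pregnancy and euploid transfers, whereas the primary outcome is now live birth and the comparison is between randomised arms.

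**What to change.** Keep the sample size. The opening section on changes to the registration dates data collection from February 2018, after the last transfer, so recruitment is not in question. Once the per-arm and two-sided readings are confirmed, restate the paragraph along these lines:

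> With 74 per arm and a two-sided 5% chi-square test, power is about 70% for a 20-point difference and about 41% for the 14-point difference seen at the centre (66% v 52%). The difference from 52% detectable with 80% power is about 22 points. The cited rates are for ongoing pregnancy, not live birth, and 66% applies to euploid transfers only, so the difference between the randomised arms may be smaller than 14 points. A non-significant result does not rule out a 14-point difference.

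Give the reason for the 20-point target, or delete it. If a one-sided test was intended, say so in both the Statistics and Sample size calculation sections; power for 14 points is then about 53%.

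The cost is one rewritten paragraph and a less favourable stated power. No patients, outcomes or analyses change.

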## Objectives

The primary objective of this RCT will be to investigate whether PGT for aneuploidy as a blastocyst selection method is superior to standard morphology scoring blastocyst selection, comparing the reproductive outcomes in FET cycles. The decision to transfer all blastocysts in FET will eliminate any potential impact of ovarian stimulation confounding on endometrial receptivity and to use freeze-all cycles will allow the use of the primary blastocysts of blastocyst cohorts. The primary outcome measure of this trial will be LB, with a LB defined as a pregnancy cycle delivering at >20 weeks of gestation.

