## **Randomisation**

Patient couples who satisfy the inclusion criteria and who completed an informed consent will randomized by computer generated number in a 1:1 ratio on day 5 of in vitro embryo culture to the two arms, with the FET drug prescription indicating allocation to the ***the PGT group***, in which all blastocysts will be assessed according to standard morphological parameters, with the best scoring blastocyst to undergo biopsy and PGT for aneuploidy or ***the morphology group***, in which all blastocysts will be assessed according to standard morphological parameters, with the best scoring blastocyst selected for transfer (figure 1). Patient couples in the PGT group will be subgrouped

according to whether the blastocyst biopsied is predicted to be euploid (**the euploid subgroup**) or aneuploid (**the aneuploid subgroup**). In the aneuploid group the next best morphology scoring blastocyst will be transferred.

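### The 80% power claimed for 74 patients holds, from either stated centre rate, only as a per-arm, one-sided figure; with the planned chi-square test read as two-sided it is about 70%

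*Combined protocol and SAP*

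**What the plan says.** The sample size paragraph gives two rates from the centre's own experience: "overall ongoing pregnancy rate was 66% for the transfer CCS euploid blastocysts, while the overall ongoing pregnancy rate was 52% for blastocysts" chosen on morphology. It then says that the number required for an "80% chance of detecting a difference of 20% at a significance level of 0.05 was calculated to be 74". The two quoted rates are 14 points apart, not 20, and no pair 20 points apart is written down. Sidedness is not given, nor whether 74 is per arm or in total.

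The Statistics section says "Categorical data were analyzed using either the chi-square test or Fisher's Exact-test", the latter for low numbers, and that p<0.05 "indicated outcomes of significant difference". It names no one-sided test. The Objectives section asks "whether PGT for aneuploidy as a blastocyst selection method is superior to standard morphology scoring blastocyst selection", which is directional wording but does not specify a test.

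Two other statements bear on the rates. Under Randomisation, "In the aneuploid group the next best morphology scoring blastocyst will be transferred". Under Outcome measures, "The primary outcome measure recorded will be LB (changed from ongoing pregnancy").

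**The concern.** A 20-point difference between proportions near the middle of the range usually needs more than 90 patients per arm for 80% power at a two-sided 5% level, so 74 looks too small for the test the plan describes.

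This is the only power statement for the primary comparison, and readers will use it to interpret a non-significant result. Told that power was 80%, they may take a null result as evidence against a useful effect. With 74 per arm and both observed rates near 52%, the 95% confidence interval around a zero difference runs to about ±16 points, so it still contains the 14-point gap seen at the centre.

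**Working it through.** **Inputs.** From the sample size paragraph: α = 0.05, power 80%, difference 20% (read as percentage points), n = 74, centre rates 52% (morphology) and 66% (euploid transfer). From Randomisation: 1:1 allocation. From Statistics: chi-square test. *Assumption:* the 20-point pair is built on one of the stated rates, either up from 52% (52 vs 72) or down from 66% (46 vs 66).

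**Formulas** (pooled normal approximation, no continuity correction; p̄ is the mean of the two rates, d their difference):

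- n per arm = [z_α √(2p̄(1−p̄)) + z_β √(p₁(1−p₁)+p₂(1−p₂))]² / d²
- power = Φ{[d√n − z_α √(2p̄(1−p̄))] / √(p₁(1−p₁)+p₂(1−p₂))}

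Here z_β = 0.8416, and z_α = 1.6449 one-sided or 1.9600 two-sided.

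**Step 1: reproduce 74.** For 52 vs 72, p̄ = 0.62, √(2×0.62×0.38) = 0.6864 and √(0.2496+0.2016) = 0.6717.

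- One-sided: (1.6449×0.6864 + 0.8416×0.6717)² / 0.04 = 71.8
- Two-sided: (1.9600×0.6864 + 0.8416×0.6717)² / 0.04 = 91.3

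For 46 vs 66, p̄ = 0.56 and the two roots are 0.7020 and 0.6876. This gives 75.1 one-sided and 95.5 two-sided. The one-sided per-arm results lie on either side of 74. The two-sided results do not come near it, and neither does the unpooled two-sided formula (88.5 and 92.8). With continuity correction, the one-sided sizes are 82 and 85.

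**Step 2: power at 74 per arm.** For 52 vs 72, d√n = 0.20×8.602 = 1.7205.

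- Two-sided: Φ[(1.7205 − 1.3454)/0.6717] = Φ(0.558) = 71.2%
- One-sided: Φ[(1.7205 − 1.1291)/0.6717] = Φ(0.880) = 81.1%

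The other cells follow in the same way. The second figure in each cell is from exact binomial enumeration of the chi-square test.

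| Rates | n per arm | Two-sided 5% | One-sided 5% |
|---|---|---|---|
| 52 vs 72 | 74 | 71.2% / 72.0% | 81.1% / 82.1% |
| 46 vs 66 | 74 | 69.2% / 71.3% | 79.5% / 80.9% |
| 52 vs 72 | 37 (74 total) | 42.4% / 41.9% | 55.2% / 57.5% |
| 46 vs 66 | 37 (74 total) | 40.8% / 40.2% | 53.6% / 53.8% |
| 52 vs 66 (centre) | 74 | 40.9% / 42.6% | 53.5% / 55.7% |

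If Fisher's exact test were used at 74 per arm, two-sided power for the two 20-point pairs would be about 65–66%.

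**Step 3: detectable difference.** At 74 per arm, a two-sided test reaches 80% power at 22.1 points up from 52%, or 22.7 points down from 66%.

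**Step 4: precision.** With 52% in both arms, the 95% half-width is 1.96 × √(2×0.52×0.48/74) = 16.1 points.

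**Step 5: the 14-point gap is itself favourable.** The 66% describes euploid transfers only, whereas PGT-arm patients with an aneuploid result receive an untested blastocyst. The document does not give the euploid share. As an illustration only, suppose that untested transfers succeed at 52%. A share of 80% then leaves 0.80×14 = 11.2 points (power 28–30% two-sided), and a share of 50% leaves 7.0 points (13–15%). The conclusion does not rest on this step.

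**The case against.** The strongest reply is that no arithmetic error has been proved. The figure 74 fits a one-sided per-arm calculation, the objective is worded as superiority, and the inputs actually used are unknown. Two-sided fits also exist at higher base rates: 64 vs 84 needs 74.3 per arm, 65 vs 85 needs 72.4, and 66 vs 86 needs 70.4, with 82–83% power at 74 per arm. It is right that the inputs are unknown and that a one-sided intention is possible. But 64 vs 84 and 65 vs 85 use neither rate in the paragraph, and 66 vs 86 makes the euploid-transfer rate the lower of the two. Superiority wording does not make a chi-square test at p<0.05 one-sided.

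A second reply is that a correctly sized trial would have the same interpretive problem: at 92 or 96 per arm the half-width is still 14.4 or 14.1 points, just including the 14-point gap. That is true. The wide interval comes partly from choosing a 20-point target, and the ±16-point figure therefore illustrates the consequence without proving the error. The power figures are unaffected.

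A third reply is that the document dates the start of data analysis to April 2018, so only text can change, and the interval should guide interpretation anyway. This limits the remedy to wording but does not make the stated power correct. Finally, the plural in the sample size sentence favours the per-arm reading. That is fair, but one added word would settle it.

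**Conclusion.** The concern holds. From either rate the paragraph states, 80% power with 74 requires both a per-arm reading and a one-sided 5% test, and the document declares no one-sided test. Under the natural two-sided reading of the planned chi-square test, power at 74 per arm is 69–72% for 20 points, about 10 points below the claim, and 92–96 per arm (pooled formula) would be needed for 80%. If 74 is the total, power is 40–42% two-sided and 54–57% one-sided. For the centre's own 66% vs 52% it is 41–43% two-sided and 53–56% one-sided at 74 per arm.

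This rests on three assumptions: the 20% is absolute, the pair is anchored on 52% or on 66% as the PGT rate, and the test is two-sided. All rates are for ongoing pregnancy, so none of these figures is a power for live birth, the current primary outcome. The stated power should be corrected.

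**What to change.** In Statistics, state that tests are two-sided. In the sample size paragraph, confirm that 74 is per arm and replace the final sentence with the text below. The existing sentence may be kept beside it as a record of the calculation made, provided it is labelled as such.

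> With 74 patients per arm and a two-sided 5% chi-square test, power is about 70% for an absolute difference of 20 points (52% vs 72% or 46% vs 66%), and about 41–43% for the centre's rates of 66% and 52% if every PGT-arm transfer performs like a euploid transfer. These figures are for ongoing pregnancy; the primary outcome is now live birth. A non-significant result does not by itself exclude a difference of the size seen at the centre.

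If a one-sided 5% test was intended, both sections must say so, and the paragraph must still report the 53–56% power for 66% vs 52%. If 74 is the total, report 40–42% two-sided for 20 points instead.

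The cost is one reworded paragraph and one added statement of sidedness. On the two-sided reading, the stated power falls from 80% to about 70%. No extra patients are needed or proposed.
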